In Arm 1, eligible participants will be treated with escalating doses of RP-3467 monotherapy, preceded by a 2-day PK run-in, to evaluate the safety and tolerability, PK, and pharmacodynamics of RP-3467 monotherapy. The cycle length will be 21 days. Evaluation of escalating doses of RP-3467 in combination with olaparib in Arm 2 will occur in parallel with Arm 1. The starting RP-3467 dose for the combination in Arm 2 will be at least one dose level lower (DL-1) than the highest monotherapy dose level evaluated and considered tolerated/safe by the Safety Review Committee (SRC).

Following disease progression, participants in the monotherapy arm will have the opportunity to receive the combination of RP-3467 and olaparib at the highest previously evaluated dose level of the combination deemed safe and tolerable (or at the preliminary RP2D if previously determined), provided they meet all required eligibility criteria, have not had Grade >2 drug-related toxicities at their current monotherapy dose, and following discussion with and approval by the Medical Monitor.

A starting Arm 1 dose level of 160 mg once daily (QD) for RP-3467 monotherapy was chosen based on preclinical Good Laboratory Practice (GLP) safety data. *In vitro* data suggest RP-3467 may be a weak cytochrome P450 (CYP) 3A inhibitor and inducer; thus, due to an unclear potential for drug-drug interactions (DDI) and confounding toxicities from olaparib alone, a starting dose of 200 mg twice daily (BID) olaparib, a lower dose than the United States Prescribing Information (USPI) recommended dose of 300 mg BID, will initially be evaluated in Arm 2 (DL-1a). Once safety and tolerability of the combination is confirmed and PK data reviewed from the initial Arm 2 cohort(s), the olaparib dose may be increased to 300 mg BID for subsequent cohorts (e.g., DL-1b).

Dose escalation and de-escalation decisions will be based on Boin criteria. The decision to escalate either RP-3467 or olaparib following the first dose level of Arm 2 will be based on [REDACTED] safety data and agreed upon by the SRC. The exposure of olaparib and RP-3467 from the first combination cohort in Arm 2 will be evaluated and used to inform the dose selection of the next combination dose level. Specifically, the RP-3467 dose will be escalated to a level that is not expected to exceed the exposure of the dose of RP-3467 monotherapy which has been cleared by the SRC. [REDACTED]

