The BOIN design will guide dose level escalations/de-escalations using the following rules for both Arm 1 (RP-3467 monotherapy) and Arm 2 (RP-3467 with olaparib), targeting a 25% DLT rate:

- If the observed DLT rate at the current dose is ≤ 0.197 , escalate the dose to the next higher dose level;
- If it is > 0.298 , de-escalate the dose to the next lower dose level;
- Otherwise, stay at the current dose.

A 3+3 decision criteria will be applied if the number of participants treated at the current dose is 3. Meaning, if 0/3 participants experience a DLT at the current dose, then the dose will be escalated. If 1/3 participants experience a DLT, then the dose will stay at the current level, and the dose will de-escalate if $\geq 2/3$ participants experience a DLT. The rules for dose escalation/de-escalation can be summarized in the following table.

Table 2: Dose Escalation/De-Escalation Rules for the BOIN Design

Action	Number of DLT Evaluable Participants at Current Dose Level								
	1	2	3	4	5	6	7	8	9
\uparrow if number of DLT \leq	0	0	0	0	0	1	1	1	1
\downarrow if number of DLT \geq	1	1	2*	2	2	2	3	3	3
Elim if number of DLT \geq	NA	NA	3	3	3	4	4	4	5

BOIN = Bayesian optimal interval; \uparrow = increase, \downarrow = decrease, DLT = dose-limiting toxicity, Elim=eliminate, NA = not applicable, dose cannot be eliminated until at least 3 participants have been treated and are DLT evaluable
Note: # of DLT is the number of participants with at least 1 DLT. When none of the actions (i.e., escalate, de-escalate or eliminate) is triggered, stay at the current dose for treating the next cohort of participants.

* Based on the 3+3 design run-in.

If a determination is made to eliminate based on the criteria in Table 2, then the current dose and all higher concentrations are eliminated, and the dose is automatically de-escalated one level. If none of the actions (escalation, de-escalation, elimination) are triggered, participants will continue to be enrolled at the current dose. Dose escalation/de-escalation will continue until the maximum total sample size is reached (n~36), 9 participants are enrolled at the current dosing level and the decision is made to maintain the current dose according to the rules outlined in Table 2, or the SRC decides to stop.

Monotherapy dose escalation may be stopped before establishment of an MTD if

- MTD is exceeded in the combination dose-escalation arm

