4.1 DLT Evaluable Population

The DLT Evaluable Population will consist of participants who have met the minimum safety evaluation requirements of the trial and /or who experience a DLT at any time during the DLT evaluation period (from the start of treatment through the end of Cycle 1). Minimum safety requirements will be met if, during Cycle 1 of treatment, the participant receives at least 75% of their planned total dose of RP-3467 and olaparib (if applicable), completes required safety evaluations and is observed through the end of Cycle 1 since the first dose of trial intervention. Administration of growth factors or transfusions during the DLT evaluation period for hematologic events not meeting DLT criteria will render a participant not DLT evaluable. DLT evaluability will be recorded in the appropriate CRF and used to determine the DLT evaluable population. The DLT evaluable population will be used to determine DLT rate of the dose levels.

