5. DEFINITIONS AND CONVENTIONS FOR DATA HANDLING

All analyses will be performed using SAS® Version 9.4 or higher.

Unless specified otherwise, the analyses of data collected will be descriptive and summaries will be presented separately for each dose level, dose schedule (if applicable) and in total for the specified analysis population. Statistical analysis will be purely descriptive and no formal hypothesis testing or comparative analysis between dose level will be performed. Confidence intervals (CIs) will be constructed at two-side 95% level where appropriate.

Frequency distributions for categorical variables will be provided as the number of subjects in the category and the percentages of the total number of subjects in the given population as noted. Percentages will be reported to one decimal place.

The descriptive statistics for continuous variables will be the number of subjects, mean, standard deviation, median, lower and upper quartile, minimum and maximum. Mean, median will be reported to 1 decimal place, while the standard deviation will be reported to 2 decimal places. Minimum and maximum will be reported the same as the original data.

Summary tables may be replaced with listings when appropriate. For instance, an AE Frequency table may be replaced with a listing if it only contains a few unique PTs reported on relatively few subjects.

All tables will be summarized by treatment regimen (Arm 1 and Arm 2 respectively), dose level, and dose schedule, and include an overall column for Arm 1 and Arm 2 respectively unless otherwise specified.

All listings will be sorted by arm, dose level, and dose schedule if applicable, subject ID and, if applicable, by visit date unless otherwise specified in the text.

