10.2 Adverse Events

All reported AEs will be coded using the Medical Dictionary for Regulatory Activities (MedDRA) with the most current version for the purposes of summarization. NCI CTCAE Version 5.0 will be used for grading AEs. AEs will be collected and recorded for each patient from the day of signing the ICF until 30 days after last trial intervention administration or until participant started alternative anticancer therapy, whichever is sooner. Prior to receiving trial intervention, only AEs considered related to trial procedures and all SAEs will be summarized by arm, dose level, and dose schedule.

A treatment-emergent adverse event (TEAE) will be defined as any event that was not present prior to the initiation of trial intervention(s) or any event that worsens in either intensity or frequency following exposure to trial intervention(s) through 30 days after cessation of trial treatment, or until the participant starts alternate anti-cancer therapy, or the participant is taking the monotherapy treatment and starts the co-therapy olaparib, whichever occurs first. The exception are RP-3467 related SAEs which were reported until the end of trial and will be included as TEAE regardless of time of onset.

All AEs reports will be summarized by treatment regimen (Arm 1 and Arm 2), dose level and schedule (if applicable) unless otherwise specified.

Overall AE summaries will be presented for the Safety Population (unless otherwise specified). The summaries will include the following categories:

- All TEAEs
- TEAEs with CTCAE Grade 3
- TEAEs with CTCAE Grade 4
- TEAEs with CTCAE Grade 5
- DLT (based on DLT evaluable population)
- RP-3467 related TEAE
 - RP-3467 related TEAE with CTCAE Grade 3
 - RP-3467 related TEAE with CTCAE Grade 4
 - RP-3467 related TEAE with CTCAE Grade 5
- Olaparib related TEAE
 - Olaparib related TEAE with CTCAE Grade 3
 - Olaparib related TEAE with CTCAE Grade 4
 - Olaparib related TEAE with CTCAE Grade 5
- Any Serious AEs
- Any treatment-emergent serious AEs (TESAE)
- RP-3467 related TESAEs
- TEAE leading to dose reduction
- TEAE leading to dose interruption
- TEAE leading to study drug withdrawal
- RP-3467 related TEAE leading to dose reduction
- RP-3467 related TEAE leading to dose interruption

- RP-3467 related TEAEs leading to study drug withdrawal
- Olaparib related TEAE leading to dose reduction
- Olaparib related TEAE leading to dose interruption
- Olaparib related TEAE leading to study drug withdrawal

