11. INTERIM ANALYSIS

Due to the exploratory nature of this Phase 1 trial, data will be assessed descriptively on an ongoing basis after each dose cohort based on safety and clinical activity information to inform the dose selection. No formal statistical inference will be made to these interim evaluations.

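### Adverse events after Arm 1 participants cross over to RP-3467 plus olaparib have no rescue-period safety summary: most fall outside the TEAE tables, and RP-3467-related SAEs may land in the monotherapy column

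*Protocol*

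**What the plan says.** - **Crossover.** Protocol 1.1 (Overall Design) provides for treatment once the disease has progressed: "participants in the monotherapy arm will have the opportunity to receive the combination of RP-3467 and olaparib at the highest previously evaluated dose level". That level must have been considered safe and tolerable; the preliminary RP2D is the alternative if there is one. A later paragraph of the same synopsis, on treatment after progression, makes that level an upper limit and ties the dose to how the participant tolerated monotherapy.
- **DLT window.** SAP 4.1 sets it "from the start of treatment through the end of Cycle 1". The visible text opens no new window at crossover.
- **TEAE window.** SAP 10.2 ends it 30 days after treatment stops, at alternative anticancer therapy, or when "the participant is taking the monotherapy treatment and starts the co-therapy olaparib, whichever occurs first". SAP 5.2 closes the treatment-emergent period at the same point. One exception stands in 10.2: serious events related to RP-3467 count as TEAEs whenever they begin.
- **Rescue period.** SAP 5.3 defines it from the first olaparib dose to treatment discontinuation. Its only later visible use is in 6.6.6, where relative dose intensity stops at its start.
- **Presentation.** SAP 5 and 10.2 summarise by arm, dose level and schedule. SAP 5 adds that "no formal hypothesis testing or comparative analysis between dose level will be performed", so these descriptive tables are the analysis.
- **Objective.** Protocol 1.1 and SAP 3.1.1 make the safety of RP-3467, alone and combined, the primary objective. DLTs and TEAEs are the primary endpoints. The end of SAP 2.1 says that the safety assessment will draw on every participant.

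**The concern.** A participant who crosses over starts contributing information on the combination at the first olaparib dose. That is the moment at which the SAP stops counting that participant's events as treatment-emergent. Closing the monotherapy window there is sensible, because it keeps combination toxicity out of the Arm 1 columns. But the visible SAP then opens no other summary for those events, although it has already named and dated the period they fall in.

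Two things are at stake. First, part of the combination experience is missing from the tables that report the primary endpoint, which does not fit the statement in SAP 2.1 about all participants. Second, the exception for RP-3467-related serious events works against the purpose of the cut. Such an event on the combination remains a TEAE of a participant assigned to Arm 1, and no rule keeps it out of that participant's monotherapy dose column. The most serious combination events could then be read as monotherapy toxicity.

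**Working it through.** **1. The plan's own counts.** SAP 2.3 gives about 12 participants in Arm 1, about 24 in Arm 2 escalation and 16 in backfill: 12 + 24 = 36, and 36 + 16 = 52. Both totals agree with the stated figures.

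**2. Where an event after crossover goes under SAP 5.2, 5.3 and 10.2.**

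| Event beginning after the first olaparib dose | In the TEAE summaries? | Elsewhere |
|---|---|---|
| Non-serious, any grade or attribution | No | Patient listing |
| Serious, related to olaparib only | No | Listing; possibly the general serious-AE row |
| Serious, related to neither drug | No | Listing; possibly the general serious-AE row |
| Serious, related to RP-3467 | Yes, column not specified | Listing |
| Fatal, not related to RP-3467 | No; outside the row for TEAEs leading to death | Listing; possibly the general serious-AE row |

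The general row is marked as possible because 10.2 lists serious AEs separately from treatment-emergent serious AEs, without saying which column a crossover's event takes.

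**3. The olaparib-related rows.** An event caused by olaparib cannot begin before olaparib starts, and for an Arm 1 participant the TEAE window closes at that start. So a crossover can add to the olaparib-related TEAE rows only through the exception, that is, with a serious event also attributed to RP-3467.

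**4. Laboratory and ECG data.** The shift tables in SAP 10.3 and 10.5 take the worst value within the treatment-emergent period, so they inherit the same cut. Section 10.3 also mentions visits up to 30 days past the last dose, but does not say how that applies to a crossover. Neither section sets out a rescue-period summary.

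**5. Size.** The documents give no crossover rate, so the number crossing over, *k*, is an assumption, ranged up to the planned Arm 1 size. Share of combination-treated participants = *k*/(24 + *k*) in escalation, and *k*/(24 + 16 + *k*) with backfill, which SAP 2.1 attaches to Arm 2.

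| *k* (assumed) | Escalation only | With backfill |
|---|---|---|
| 3 | 3/27 = 11% | 3/43 = 7% |
| 6 | 6/30 = 20% | 6/46 = 13% |
| 9 | 9/33 = 27% | 9/49 = 18% |
| 12 | 12/36 = 33% | 12/52 = 23% |

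**The case against.** The strongest reply is that crossovers are well protected and their events are not lost. Entry requires eligibility, no related toxicity above Grade 2 on the current monotherapy dose, and Medical Monitor approval. The dose is limited to a combination level cleared by the SRC. Stopping for intolerance or risk applies to everyone. AEs are collected to 30 days after the last dose, all AEs and SAEs are listed by patient, and MDS/AML is listed in detail (SAP 10.2). SAP 11 says "data will be assessed descriptively on an ongoing basis after each dose cohort", and nothing visible excludes crossover data from that review. All of this stands.

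A reader might therefore infer too much in three ways.

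- *That crossovers are treated outside every toxicity rule, or that the SRC will not see their events.* The safeguards above contradict the first. The second does not follow from the lack of a numerical boundary.
- *That leaving crossovers out of the DLT count is an error.* It is defensible, because they are pretreated with RP-3467 and selected for tolerating it. SAP 6.6.3 excludes intraparticipant escalators from the DLT-evaluable set at their new dose. What is missing is the equivalent sentence for crossover.
- *That the escalation rules would often have been overturned.* Suppose a level with a true DLT rate of 40% clears at 0/3 (0.6³ = 21.6%) and six crossovers follow. The pooled rate over nine then exceeds 0.298 (at least 3 events) with probability 45.6%, but jointly only 0.216 × 0.456 = 9.8%. At a 50% rate the joint figure is 0.125 × 0.656 = 8.2%. Six at one level is an assumption. At a 40% rate, given 0/3, one crossover gives 0% (1/4 = 0.25), two give 16% and three give 35%. Applying an Arm 2 rate to people selected for tolerance is also unsupported. These figures do not measure the gap.

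Listings do not answer the reporting point, since they give no incidence by combination dose level.

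**Conclusion.** The concern holds as a reporting gap in the SAP. In the visible text the TEAE window closes at the first olaparib dose, and the rescue period that begins there has no AE, laboratory or ECG summary. Crossover toxicity on the combination reaches the TEAE tables only as RP-3467-related serious events, with no rule on the column. For 3 to 12 crossovers (assumed), the affected group is 11% to 33% of combination-treated participants in escalation, or 7% to 23% with backfill. These are shares of participants; the documents do not allow an estimate of how many events would be affected.

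The documents do not support a claim that crossovers are unmonitored or that escalation decisions are invalid.

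The finding is limited to visible text. Only the protocol synopsis is available, SAP sections 7 to 9 do not appear, and there are redactions beside the post-progression paragraph of the synopsis and within the DLT timing sentence of SAP 10.1. A crossover rule could sit in any of these places; if so, SAP 10.2 needs only a cross-reference.

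**What to change.** 1. Add to SAP 10.2 a rescue-period AE summary by combination dose level, separate from Arms 1 and 2: all events, Grade 3 or higher, serious, related to each drug, leading to discontinuation, and fatal.
2. Define rescue-emergent events as those beginning or worsening from the first olaparib dose until 30 days after the last dose or the start of new anticancer therapy, whichever is first. SAP 5.3 ends the rescue period at treatment discontinuation, so the 30-day tail used elsewhere has to be stated.
3. Assign RP-3467-related SAEs that begin after crossover to this table and not to the Arm 1 monotherapy column.
4. State in SAP 4.1 that crossovers are not DLT-evaluable at the combination level, parallel to SAP 6.6.3.
5. Include the table in the data given to the existing SRC.
6. Reconcile the two synopsis statements on the crossover dose, one placing it at the highest level and the other up to it. Which is intended is for the sponsor to say.

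No new DLT window and no numerical trigger are proposed. The cost is a few sentences of SAP text and one small descriptive table from data already collected. The table will describe a pretreated, selected group and should be labelled so, because its rates are not comparable with those of Arm 2.

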TEAE	Treatment-emergent adverse events
TL	Target lesion
T _{max}	Time to maximum observed plasma concentration
t _{1/2}	Elimination half-life
ULN	Upper limit of normal
VAF	Variant allele frequency

1. INTRODUCTION

This document describes the statistical methods to be implemented in the statistical analysis of data collected under clinical study Protocol RP-3467-01, titled: "Phase 1 Trial of the Safety, Pharmacokinetics, Pharmacodynamics, and Preliminary Clinical Activity of RP-3467 Alone and in Combination with Olaparib in Participants with Advanced Solid Tumors (POLAR Trial)". This Statistical Analysis Plan (SAP) contains definitions of analysis populations, derived variables, statistical methods for the analyses of baseline, [REDACTED] and safety data and the data listings and summary tables which will be produced. Details will be described to ensure the results are complete and appropriate to allow valid conclusion regarding the study objectives.

The analysis details for pharmacokinetic, pharmacodynamics, and biomarker analyses are not described within this SAP. A separate analysis plan may be implemented for those analyses.

This document has been prepared based on Protocol Version 2.0, dated July 17, 2024.

2. STUDY OVERVIEW

This is a multicenter, open-label Phase 1 trial to investigate the safety, [REDACTED] pharmacodynamic, and preliminary efficacy of the Pol θ inhibitor RP-3467 alone or in combination with the poly-ADP ribose polymerase (PARP) inhibitor (PARPi) olaparib in participants with molecularly selected advanced solid tumors. The trial is estimated to enroll approximately 52 evaluable participants with any of the following types of tumors:

- Locally advanced or metastatic epithelial ovarian cancer (including fallopian tube or primary peritoneal)
- Metastatic breast cancer
- Metastatic castration-resistance prostate cancer (mCRPC)
- Pancreatic adenocarcinoma

In addition, these participants harbor any one of the following in their biomarker profile:

- Deleterious alteration of BRCA1/2, PALB2, RAD51B/C/D
- Homologous recombination deficiency (HRD+)

Preclinical studies demonstrate that Pol θ inhibition sensitizes HR deficient cells to PARPi which is consistent with reliance on microhomology or theta mediated end joining (MMEJ) by homologous recombination (HR) deficient tumors.

2.1 Study Design

The trial will follow a Bayesian Optimal Interval (BOIN) design to guide escalation and de-escalation decision for both monotherapy (Arm 1) and combination therapy (Arm 2) respectively, to establish a maximum tolerated dose (MTD) or maximum administered dose (MAD), and to identify a dose of RP-3467 alone and in combination with olaparib that is tolerable.

[REDACTED]

[REDACTED]

The starting dose (Dose Level 1) for Arm 1 is 160 mg once daily (QD). The starting dose for RP-3467 in Arm 2 will be at least one level lower than the highest monotherapy dose level considered safe by the SRC. The starting dose of olaparib will be 200 mg twice a day (BID). Once safety of olaparib used in combination with RP-3467 is confirmed, the dose of olaparib may be increased to the USPI recommended dose of 300 mg BID for subsequent cohorts.

Escalation in Arm 1 (monotherapy) will proceed with up to 100% increases in RP-3467 after evaluation of tolerability by the SRC until Dose Level N. Dose Level N is defined as the dose level at which any of the following safety signals occur:

- Any \geq Grade 3 hematological toxicity
- $>50\%$ decrease in platelets or neutrophils from the first dose
- >2 g/dL decrease in hemoglobin from the first dose
- Any \geq Grade 2 drug-related non-hematological toxicity lasting >5 days or requiring clinical intervention, except Grade 2 fatigue, nausea, vomiting, diarrhea, or constipation
- Any adverse event (AE) of any grade limiting tolerability as assessed by the SRC

After dose level n is reached, subsequent dose levels of RP-3467 may be increased by 75% or a modified Fibonacci sequence per SRC discretion based on the safety profile observed.

Dose escalations in Arm 2 (RP-3467 with olaparib) will be guided by dose levels in Arm 1(RP-3467 monotherapy). The same criteria guiding dose escalations in Arm 1 will be used to determine escalations of RP-3467 in Arm 2 if the events occur during the DLT evaluation period.

Once a dose level is reached that results in maximally efficacious RP-3467 exposure in Arm 2: RP-3467 with olaparib, this dose level may be expanded to at least 6 participants to better assess safety/tolerability

[REDACTED].

Table 1: Dose Levels of RP-3467

Dose Level	Arm 1	Arm 2	Escalation Plan
	RP-3467 Daily (mg)^a or % of previous dose	RP-3467 Daily (mg)^a	Olaparib (mg, BID)
-1a	NA	80	200
-1b ^b			300 ^b
1	160	RP-3467 dose not higher than corresponding Arm 1 DL	300
2	Up to 100% increase until level N		300

The BOIN design will guide dose level escalations/de-escalations using the following rules for both Arm 1 (RP-3467 monotherapy) and Arm 2 (RP-3467 with olaparib), targeting a 25% DLT rate:

- If the observed DLT rate at the current dose is ≤ 0.197 , escalate the dose to the next higher dose level;
- If it is > 0.298 , de-escalate the dose to the next lower dose level;
- Otherwise, stay at the current dose.

A 3+3 decision criteria will be applied if the number of participants treated at the current dose is 3. Meaning, if 0/3 participants experience a DLT at the current dose, then the dose will be escalated. If 1/3 participants experience a DLT, then the dose will stay at the current level, and the dose will de-escalate if $\geq 2/3$ participants experience a DLT. The rules for dose escalation/de-escalation can be summarized in the following table.

Table 2: Dose Escalation/De-Escalation Rules for the BOIN Design

Action	Number of DLT Evaluable Participants at Current Dose Level								
	1	2	3	4	5	6	7	8	9
\uparrow if number of DLT \leq	0	0	0	0	0	1	1	1	1
\downarrow if number of DLT \geq	1	1	2*	2	2	2	3	3	3
Elim if number of DLT \geq	NA	NA	3	3	3	4	4	4	5

BOIN = Bayesian optimal interval; \uparrow = increase, \downarrow = decrease, DLT = dose-limiting toxicity, Elim=eliminate, NA = not applicable, dose cannot be eliminated until at least 3 participants have been treated and are DLT evaluable
Note: # of DLT is the number of participants with at least 1 DLT. When none of the actions (i.e., escalate, de-escalate or eliminate) is triggered, stay at the current dose for treating the next cohort of participants.

* Based on the 3+3 design run-in.

If a determination is made to eliminate based on the criteria in Table 2, then the current dose and all higher concentrations are eliminated, and the dose is automatically de-escalated one level. If none of the actions (escalation, de-escalation, elimination) are triggered, participants will continue to be enrolled at the current dose. Dose escalation/de-escalation will continue until the maximum total sample size is reached (n~36), 9 participants are enrolled at the current dosing level and the decision is made to maintain the current dose according to the rules outlined in Table 2, or the SRC decides to stop.

Monotherapy dose escalation may be stopped before establishment of an MTD if

- MTD is exceeded in the combination dose-escalation arm

Intrapatient dose escalations of RP-3467 or olaparib (from 200 mg BID to 300 BID) may be allowed at the discretion of the investigator and with Sponsor approval.

Once an MTD [REDACTED] has been established for Arm 2: RP-3467 with olaparib, backfill cohorts up to 8 evaluable participants may be enrolled. The objectives of the backfill cohorts are to aid in the assessment of antitumor activity, [REDACTED] and further optimize dose.

After the trial is completed, results from all participants including the backfill cohorts will be included to assess safety. The MTD can be determined based on the isotonic estimate of the toxicity that is closest to the target toxicity.

